5.3 Method of Assignment to Treatment

Patients who meet all criteria for enrollment will be randomized in a 1:1:1 ratio (baricitinib 4-mg; baricitinib 2-mg; placebo) to double-blind treatment at Visit 2 (Week 0). Randomization will be stratified by disease activity (total Systemic Lupus Erythematosus Disease Activity Index 2000 [SLEDAI-2K] <10; \geq 10), corticosteroid dose (<10 mg/day; \geq 10 mg/day prednisone or equivalent at baseline), and region as given in [Table JAIA.5.1](#).

Assignment to treatment groups will be determined by a computer-generated random sequence using an IWRS. The IWRS will be used to assign packages containing double-blind investigational product to each patient, starting at Visit 2 (Week 0), and at each visit subsequent through Visit 15 (Week 48).

Table JAIA.5.1. Countries and Associated Geographical Regions

Geographical Region	Country or Countries
North America	United States
Central, South America and Mexico	Argentina, Chile, Colombia
Europe	France, Italy, Poland, Romania, Spain
Asia	Japan, Korea, Philippines
Rest of World	India, Serbia, South Africa

6 A Priori Statistical Methods

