6.3 Definition of Baseline and Postbaseline Periods

For efficacy analyses (excluding daily diaries), baseline is defined as the last non-missing value prior to the first dose of study drug, unless otherwise specified. In most cases, this will be the measurement recorded at Week 0 (Visit 2).

Baseline for the safety analyses is defined as:

- The last non-missing scheduled (planned) measurement prior to the first dose of the study drug for continuous measures by-visit analyses, and
- All non-missing measurements prior to the first dose of the study drug for all other analyses.

In general, for efficacy and safety (except adverse events) analyses, when the baseline measurement is collected on the same day (where time is not collected) as the first dose date, this measurement will be used as the baseline value for data analysis.

Postbaseline measures for the safety analyses are defined as the non-missing scheduled (planned) measurements after the first dose of the study drug for continuous measures by-visit analyses and all non-missing measurements after the first dose of the study drug for all other analyses.

Postbaseline data collection begins after the first dose of study drug administration at Visit 2 (Week 0) and will continue through Visit 16 (Week 52), early study termination visit, or the follow-up visit.

The baseline value for the daily diary assessments (Worst Pain Numeric Rating Scale [NRS], Worst Joint Pain NRS, Worst Fatigue NRS, Joint Stiffness Duration, Joint Stiffness Severity NRS, and Patient Global Impression of Severity [PGI-S]) is defined as the average of the non-missing assessments in the last 7 days prior to the date of first study drug administration (expected at Week 0, Visit 2). There must be at least 4 non-missing daily measurements in the 7 days indicated. If there are less than 4 non-missing daily assessments collected prior to the date of first study drug administration, then the baseline value will be designated as missing. If there are multiple assessments collected on the same day, only the first collected record will be used.

Postbaseline values of daily diary assessments collected after first study drug administration through Visit 16, or early study termination visit, will be defined as the average of the last 7 days prior to the date of the study visit. If less than 4 non-missing daily measurements are present, the visit will be set to missing.

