Treatment comparisons of continuous efficacy and health outcome variables, except for SLICC/ACR Damage Index, Patient's Global Impression of Change and Joint Stiffness Duration, will use a restricted maximum likelihood-based MMRM analysis. The model will include the following explanatory variables as fixed factors: treatment, baseline disease activity (total SLEDAI-2K <10; ≥ 10), baseline corticosteroid dose (<10 mg/day; ≥ 10 mg/day prednisone or equivalent), region (North America, Central/South America/Mexico, Europe, Asia and Rest of World), visit (as categorical variable), baseline value, treatment-by-visit interaction, and baseline value-by-visit interaction. The response variable will be change from baseline across postbaseline visits. Within-patient errors will be modeled using an unstructured covariance structure. If the model fails to converge, the following covariance structures will be implemented in the following order: heterogeneous Toeplitz, heterogeneous autoregressive (1) heterogeneous compound symmetry, and autoregressive. The least squares (LS mean) difference, standard error, p-value, and CIs will be reported. Type III tests for the LS means will be used for the statistical comparisons.

Treatment comparisons of SLICC/ACR Damage Index will be made using analysis of covariance (ANCOVA) with baseline value as covariate. For Patient's Global Impression of Change, the analysis of variance (ANOVA) will be applied. For both models, treatment, baseline disease activity (total SLEDAI-2K <10; ≥ 10), baseline corticosteroid dose (<10 mg/day; ≥ 10 mg/day prednisone or equivalent), and region (North America, Central/South America/Mexico, Europe,

Asia and Rest of World) will be included as the categorical factors. Type III tests for LS means will be used for statistical comparison between treatment groups. The LS mean difference, standard error, p-value, and 95% CI may also be reported.

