Treatment comparisons for duration of joint stiffness will be analyzed using a nonparametric method using the Hodges-Lehmann estimator. For the comparison between each baricitinib group and placebo group, the median difference of change from baseline score and its 95% CI from the Hodges-Lehmann estimator will be presented. The p-value for the median difference of change from baseline will be calculated using the Wilcoxon rank-sum test. A 95% CI for the median change from baseline score within each treatment group will be calculated using distribution-free confidence limits.

Time to first flare analyses will be analyzed using a Cox proportional hazards model with treatment group, with disease activity (total SLEDAI-2K <10; \geq 10), baseline corticosteroid dose (<10 mg/day; \geq 10 mg/day prednisone or equivalent), and region (North America, Central/South America/Mexico, Europe, Asia and Rest of World) fitted as explanatory variables. Hazard ratios, median time to flare, 95% CI and p-values will be presented for treatment comparisons to placebo. Only if flares occurred during the flare exposure time period (defined below for each datapoint set, respectively) will be counted as an event. For severe SFI flare, only the eligible severe flares will be counted (See 6 criteria for identifying eligible severe SFI flares in [Appendix 5](#)). Patients who do not have an event during the flare exposure time period will be censored at the end of the flare exposure time. The flare exposure time varies with different datapoint sets ([Table JAIA.6.5](#)).

- For the PPCV datapoint set, while considering the treatment effect without potentially confounding influences of COVID-19, the flare exposure time is defined as the time after the date of the first dose of study drug to the prohibited medication start date, treatment discontinuation date, study discontinuation date or date of the Week 52 visit, whichever is earlier, and excluding the time period of treatment interruption due to COVID-19 from the interruption start date plus 20 days to the interruption end date plus 20 days, both inclusive, if the interruption duration is 20 days or more.

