6.4.1 Adjustments for Covariates

Randomization is stratified according to disease activity (total SLEDAI-2K at screening <10; ≥ 10), corticosteroid dose at baseline (<10 mg/day; ≥ 10 mg/day prednisone or equivalent), and region (North America, Central/South America/Mexico, Europe, Asia and Rest of World). Therefore, these factors will be adjusted for as described in Section [6.4](#).

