Corticosteroid Sparing	Proportion of patients receiving > 7.5 mg/day prednisone at baseline able to reduce prednisone (or equivalent) dose by $\geq 25\%$ to a prednisone equivalent dose of ≤ 7.5 mg/day maintained between Week 40 and Week 52 visit ^g	Logistic Regression, NRI + mLOCF	PPCV	Week 52 visit	Major secondary (Principal inference)
		Logistic Regression, NRI	PP		Supplemental
		Logistic Regression, NRI	AC		Supplemental
	Proportion of patients receiving > 7.5 mg/day prednisone at baseline able to reduce prednisone (or equivalent) dose by $\geq 25\%$ maintained between Week 40 and Week 52 visit ^g	Logistic Regression, NRI + mLOCF	PPCV	Week 52 visit	Supplemental
		Logistic Regression, NRI	PP		Supplemental
	Proportion of patients receiving > 7.5 mg/day prednisone at baseline able to reduce prednisone (or equivalent) dose to ≤ 7.5 mg/day maintained between Week 40 and Week 52 visit ^g	Logistic Regression, NRI + mLOCF	PPCV	Week 52 visit	Supplemental
		Logistic Regression, NRI	PP		Supplemental
	Change from baseline in prednisone dose	MMRM	PP	Week 52 visit	Secondary endpoint
	Proportion of patients able to discontinue corticosteroids and maintained through Week 52 visit ^h	Logistic Regression, NRI	PP	Week 52 visit	Secondary endpoint
Worst Pain NRS	Change from baseline in Worst Pain NRS	MMRM+MI	PPCV	Week 52 visit	Major secondary (Principal inference)
		MMRM	PP		Supplemental
		MMRM	AC		Supplemental

Description of Efficacy/Health Outcomes Analyses

Measure	Variable	Analysis and Imputation Method	Datapoint Sets	TPI*	Analysis Type
FACIT-Fatigue	Change from baseline in FACIT-Fatigue total score	MMRM+MI	PPCV	Week 52 visit	Major Secondary (Principal inference)
		MMRM	PP		Supplemental
		MMRM	AC		Supplemental
Worst Fatigue NRS	Change from baseline in Worst Fatigue NRS	MMRM	PP	Week 52 visit	Secondary endpoint
Worst Joint Pain	Change from baseline in Worst Joint Pain NRS	MMRM	PP	Week 52 visit	Secondary endpoint
Joint Stiffness Duration	Change from baseline in Joint Stiffness Duration	Wilcoxon rank-sum with mLOCF	PP	Week 52 visit	Secondary endpoint
Joint Stiffness Severity	Change from baseline in Joint Stiffness Severity	MMRM	PP	Week 52 visit	Secondary endpoint
Patient Global Impression of Severity	Change from baseline in Patient Global Impression of Severity	MMRM	PP	Week 52 visit	Secondary endpoint
Patient Global Impression of Change	Change from baseline in Patient Global Impression of Change	ANOVA with mLOCF	PP	Week 52 visit	Secondary endpoint

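### Joint stiffness duration is tested on raw change with no adjustment for baseline or randomisation strata: a valid test that gives away precision

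*SAP*

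**What the plan says.** SAP Section 6.4 takes joint stiffness duration out of the main model for continuous outcomes. It lists the measures that are treated differently ("except for SLICC/ACR Damage Index, Patient's Global Impression of Change and Joint Stiffness Duration, will use a restricted maximum likelihood-based MMRM analysis") and then gives this one its own method: "Treatment comparisons for duration of joint stiffness will be analyzed using a nonparametric method using the Hodges-Lehmann estimator". On testing it states: "The p-value for the median difference of change from baseline will be calculated using the Wilcoxon rank-sum test". Table JAIA.6.6 repeats the choice as "Wilcoxon rank-sum with mLOCF", on the PP datapoint set at Week 52, as a secondary endpoint. Neither place names strata, a covariate or a supporting adjusted analysis.

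Section 5.3 describes the design: "Randomization will be stratified by disease activity", corticosteroid dose and region. Section 6.4.1 draws the consequence: "Therefore, these factors will be adjusted for as described in Section" 6.4. A baseline exists for this measure. Section 6.3 defines it for the daily diaries: it "is defined as the average of the non-missing assessments in the last 7 days prior to the date of first study drug administration", with at least 4 entries required.

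**The concern.** Joint stiffness duration stands apart from the rest of Section 6.4. The logistic, MMRM, ANCOVA, ANOVA, Cox and negative binomial efficacy models all include the stratification factors. The one reduction is in Table JAIA.6.6, where corticosteroid dose leaves the model for the subset on more than 7.5 mg/day. The other two measures excepted from the MMRM keep the factors ("For both models, treatment, baseline disease activity" and the rest), and the SLICC/ACR model adds baseline. Patient's Global Impression of Change has no baseline to add, because it asks about change since the start of the study.

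Joint stiffness duration has a measured baseline, and the test uses it only by subtraction. For a duration in minutes this matters. The value cannot fall below zero, so a patient with little stiffness at entry has little room to improve, while a patient with a long duration has a lot. Ranks of raw change therefore partly rank the baseline. Conditioning on baseline removes that noise and guards against chance imbalance. At stake is the precision of one secondary comparison.

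**Working it through.** **The plan's own figures.** The SAP gives no power, standard deviation, correlation or effect size for this endpoint, so there is nothing to reproduce. Its only power figure (Section 5.2) concerns the primary endpoint: 40% v 57%, about 750/3 = 250 per arm, two-sided 0.05. With pooled proportion 0.485, z = (0.17 × √250 − 1.96 × √(2 × 0.485 × 0.515)) / √(0.40 × 0.60 + 0.57 × 0.43) = (2.688 − 1.385)/0.696 = 1.87. Power is 96.9%, which agrees with the stated >90% but does not bear on this point.

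**Variance of the two comparisons.** Let S_b and S_f be the baseline and follow-up standard deviations and r their correlation.

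- Change score: S_b² + S_f² − 2 r S_b S_f
- Baseline-adjusted: S_f² (1 − r²)
- Difference: (S_b − r S_f)², which is never negative

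With S_b = S_f the ratio of adjusted to change-score variance is (1 − r²)/(2(1 − r)) = (1 + r)/2.

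| Assumed r | Ratio (1 + r)/2 | Gain expressed as extra patients, 1/ratio − 1 |
|---|---|---|
| 0.3 | 0.65 | 54% |
| 0.5 | 0.75 | 33% |
| 0.7 | 0.85 | 18% |
| 0.8 | 0.90 | 11% |
| 0.9 | 0.95 | 5% |

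This is normal theory and only approximate for ranks.

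**Simulation on ranks.** Assumptions, none from the SAP: a 0.25 SD shift (log scale for skewed data), stratum effects with SD about 0.3, no ties, zeros or missing data, 1500 runs per cell. The layout followed the SAP: 250 per arm and 2 × 2 × 5 = 20 strata. Power:

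| Outcome, r | Wilcoxon on change | Van Elteren on change | Rank ANCOVA, baseline only | Rank ANCOVA, baseline and strata |
|---|---|---|---|---|
| Normal, 0.3 | 61% | 61% | 79% | 81% |
| Normal, 0.5 | 76% | 77% | 85% | 86% |
| Normal, 0.7 | 92% | 93% | 95% | 94% |
| Lognormal, 0.3 | 50% | 52% | 79% | 80% |
| Lognormal, 0.5 | 65% | 65% | 84% | 85% |
| Lognormal, 0.7 | 84% | 85% | 94% | 95% |

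Three results follow.

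- The planned test kept its level. Across all null cells, with and without stratum effects, its rejection rate was 2.8% to 5.7%.
- Almost all the gain comes from baseline. Stratifying the Wilcoxon test alone moved power by about −2 to +1.5 points over all cells.
- The last column ranks within strata, whereas the fix below enters the factors as main effects. The baseline-only column gives nearly the same power, so this difference matters little.

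A further simulation used skewed minutes with 0 to 40% zeros and r from 0.3 to 0.7. Rank ANCOVA gained 9 to 29 points with type I error near 5%, so ties at zero do not remove the advantage.

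**The case against.** The strongest defence is that the method is deliberate, complete and valid. The SAP excepts this measure from the MMRM, names the test, the estimator and the imputation, and repeats the choice in the analysis table. Wilcoxon and Hodges-Lehmann are also a matched pair, so the p-value and interval agree. This stands as far as validity goes. It does not explain the missing baseline covariate, since rank methods accept covariates.

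A reader might infer several stronger claims, which the documents or the algebra do not support.

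- *That Section 6.4.1 is contradicted.* It promises adjustment only as Section 6.4 describes, and Section 6.4 describes none for this measure. This is a departure from the stated principle, not a strict contradiction.
- *That baseline is ignored.* A change score uses it, with a fixed coefficient of 1.
- *That raw change is less efficient whenever r is below 1.* This needs a condition such as equal variances. The loss is zero where S_b = r S_f, which can occur with r below 1.
- *That the figures estimate this trial's loss.* Every correlation is assumed, and at r = 0.9 little is lost.
- *That a stratified Wilcoxon (van Elteren) test would do as well.* It adds almost nothing.

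The matched-pair argument also exposes a real cost. An unadjusted Hodges-Lehmann interval gets no narrower, and it can include zero when the adjusted p-value is below 0.05.

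**Conclusion.** The point holds as a small, near-free improvement. The planned analysis is valid but less precise than one that conditions on a baseline the trial already collects, and it departs from how the SAP treats its other efficacy models. Under equal variances the variance falls by 35% at r = 0.3, 15% at r = 0.7 and 5% at r = 0.9. Simulated gains were larger for skewed than for normal outcomes. All sizes rest on assumed correlations, effects and distributions.

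One might infer that the trial's conclusions are exposed. They are not: Table JAIA.4.1 places this endpoint among those without multiplicity control, and joint stiffness severity is analysed separately by the fully adjusted MMRM.

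**What to change.** In Section 6.4 and the joint stiffness row of Table JAIA.6.6, take the p-value from a rank ANCOVA. Regress the rank of the Week 52 value, with the existing mLOCF rule, on treatment, rank of baseline and the three stratification factors as main effects. Keep the Hodges-Lehmann estimate and interval as a descriptive summary labelled unadjusted. State that inference rests on the rank ANCOVA, because the two can occasionally disagree. Do not offer a van Elteren test as an alternative.

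The cost is about two sentences in Section 6.4 and one line in the table. No new data are needed, and no patients are lost, because change already requires a baseline. If treatment codes are already open, report the rank ANCOVA only as a supportive analysis, labelled as added later.

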- For the PP datapoint set, which ignores treatment interruption due to COVID-19, the flare exposure time is defined as the time after the date of the first dose of investigational product to the prohibited medication start date, treatment discontinuation date, study discontinuation date or date of the Week 52 visit, whichever earlier.
- For the As Collected (AC) datapoint set, which considers all collected data, the flare exposure time is defined as the time after the date of the first dose of investigational product to the study discontinuation date or date of the Week 52 visit, whichever earlier.

The annualized flare rate will be calculated as the number of flares divided by the flare exposure time in days multiplied with 365.25, where the flare exposure time is defined above and varies with the different datapoint sets. The number of flares includes the flare events that happened during the flare exposure time period. All collected flares, including mild/moderate and severe flares will be considered eligible for the analysis.

For comparing the flare rate in the baricitinib treatment group versus the placebo, the negative binomial regression model will be applied. The response variable in the model will be the number of flares during the flare exposure time with baseline disease activity (total SLEDAI-2K <10; ≥ 10), baseline corticosteroid dose (<10mg/day; ≥ 10 mg/day prednisone or equivalent), region (North America, Central/South America/Mexico, Europe, Asia and Rest of World) as explanatory variables. The natural logarithm of the flare exposure time will be used as an offset variable in the model to adjust for patients having different exposure times. The estimated rate ratio and the corresponding 95% CI, as well as the 2-sided p-value will be presented. When the negative binomial regression does not converge or the parameters cannot be estimated, an exact Poisson regression will be applied to calculate the rate ratio, 95% CI and the p-value.

Fisher's exact test will be used for patient disposition, adverse events (AEs), discontinuations, and other categorical safety data for between-treatment group comparisons. Continuous vital signs, body weight, and other continuous safety variables including laboratory variables will be analyzed by ANCOVA with treatment and baseline value in the model. Shift tables for select categorical safety analyses (for example, "high" or "low" laboratory results) will also be produced.

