CLASI	
The CLASI is a validated instrument to assess cutaneous manifestations of SLE consisting of 2 scores:
 
 Activity Damage 	Total Activity Score	Calculated within tablet system with edit checks; no additional derivation.	
Within tablet system: If any item scores, but not all are missing then impute a score of 0 for the missing item(s).
 
For completely missing questionnaires, data can be carried forward if obtained within 36 days of visit; otherwise missing.

		Total Damage Score	Calculated within tablet system with edit checks; no additional derivation.	
Within tablet system: if any item scores, but not all are missing then impute a score of 0 for the missing item(s).
 
For completely missing questionnaires, data can be carried forward if obtained within 36 days of visit; otherwise missing.

Description and Derivation of Efficacy/Health Outcomes Measures and Endpoints

Measure	Description	Variable	Derivation/Comment	Definition of Missing
LLDAS	The LLDAS is a composite measure designed to identify patients achieving a state of low disease activity.	LLDAS	
 SLEDAI-2K \leq 4, with no activity in SLEDAI-2K major organ systems (CNS, Vascular, Renal, Cardiorespiratory and Constitutional), where “no activity” is defined as all items of SLEDAI-2K within these major organ systems equal to 0. No new features of Lupus disease activity in SLEDAI-2K compared to previous occurred visit, where the “new feature” is defined as any of the SLEDAI-2K 24 items changed from 0 to greater than 0. PGA \leq 1 Current prednisone or equivalent \leq 7.5 mg/day 	Missing if any component remains missing after each instrument level imputation rule is applied.
SFI Flare	The SFI uses the SLEDAI score, disease activity scenarios, treatment changes, and PGA to define mild/moderate and severe flares.	SFI Flare	Not derived; used as entered.	The absence of a flare record, or ‘Not Applicable’, both are indicative of no occurrence of flare.
		Annualized Flare Rate	Calculated as the number of SFI flares divided by the flare exposure time in days multiplied with 365.25.	No minimum data requirement.
		Time to First Flare	The time to first flare will be derived as the first date of most recent flare minus date of first administration of investigational product. If the subject did not have a flare, the time to first flare will be censored at the end of the flare exposure time	No minimum data requirement.

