Two-sided p-values are often reported yet should not be over-interpreted. For safety analyses, they are used primarily as a flagging mechanism.

Exposure-adjusted incidence rates (EAIR) will be calculated by treatment group. Incidence rate difference and ratio along with 95% CI may be provided for SAEs and AESIs.

The EAIR evaluating the incidence of a first event per 100 patient-years at risk (PYR) will be provided. Exposure will be calculated based on the analysis period defined as the treatment period plus up to 30 days off-drug follow-up time. Exposure time for a patient with an event will be counted up to the time of the start of event. Exposure time for a patient without an event will be censored at the end of the analysis period.

6.13.1 *Extent of Exposure*

Duration of exposure (in days) will be calculated as follows:

- Duration of exposure to investigational product is date of last dose of study drug – date of first dose of study drug +1.

Last dose of study drug is calculated as last date on study drug. See the compound-level safety standards for more details including imputation of missing last date on study drug.

Duration of exposure to study drug will be summarized using descriptive statistics (n, mean, standard deviation [SD], minimum, first quartile, median, third quartile, maximum). Cumulative exposure and duration of exposure will be summarized in terms of frequency counts and percentages by category and treatment group.

Exposure ranges will generally be reported in weeks using the following as a general guide:

- ≥ 4 weeks, ≥ 16 weeks, ≥ 24 weeks, ≥ 52 weeks
- >0 to <4 weeks, ≥ 4 weeks to <16 weeks, ≥ 16 weeks to <24 weeks, ≥ 24 to <52 weeks, and ≥ 52 weeks

Total patient-years (PY) of exposure to study drug will be reported for each treatment group for overall duration of exposure. Overall exposure will be summarized in total PY which is calculated according to the following formula:

Total patient-years of exposures (PYE) = sum of duration of exposure in days (for all patients in treatment group) / 365.25

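### Flare exposure time ends at disposition dates rather than at the last SFI assessment, so an unassessed tail before the end date counts as flare-free time

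*SAP*

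**What the plan says.** Section 6.4 of the SAP defines a flare exposure time for each datapoint set:

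- **PPCV** (principal inference for time to first severe flare, Table JAIA.6.6): from first dose to the earliest of prohibited-medication start and "treatment discontinuation date, study discontinuation date or date of the Week 52 visit, whichever is earlier", with COVID-19 treatment interruptions of 20 days or more taken out.
- **PP** (supplemental for that endpoint): up to the "prohibited medication start date, treatment discontinuation date, study discontinuation date or date of the Week 52 visit, whichever earlier".
- **AC** (supplemental): from first dose of "investigational product to the study discontinuation date or date of the Week 52 visit, whichever earlier".

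On censoring in the Cox model it says: "Patients who do not have an event during the flare exposure time period will be censored at the end of the flare exposure time". The logarithm of the same interval is the offset in the negative binomial model for the annualized flare rates.

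On the SFI, Table JAIA.6.4 (Section 6.10.1) says of "The absence of a flare record" and of a not-applicable entry that "both are indicative of no occurrence of flare". For both time to first flare and annualized flare rate, it sets no minimum amount of data. Section 6.4.2 has no missing-data rule specific to flares.

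**The concern.** Several severe-flare criteria in Appendix 5, such as a SLEDAI score above 12 or a PGA above 2.5, can be met only if someone assesses the patient. A visit missed in mid-study may be made good at the next one, because a flare in between can still be recorded. After the last assessment nothing can be recorded. Yet the clock runs on to the listed end date, and the absence of a record is read as absence of a flare.

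Time to first severe flare is a multiplicity-controlled major secondary endpoint for both doses, and the annualized rates share the same denominator. Unassessed time lowers the estimated rates. If one arm has more of it, the comparison tilts in that arm's favour.

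Elsewhere the SAP is stricter about stale or missing assessments. A PGA value is carried forward only within 36 days (Table JAIA.6.4). Compliance for patients who leave early or are lost is based on the last completed visit with a tablet count (Section 6.8). The Safety population leaves out patients lost at the first postbaseline visit, whereas the mITT population keeps them. Such a patient may have no postbaseline SFI at all and still add flare-free time.

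**Working it through.** **The plan's own figure.** The only design figure is the power of the primary SRI-4 comparison (Section 5.2): about 750 patients at 1:1:1, so 250 per arm, 57% v 40%, two-sided alpha 0.05. Recomputed:

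- Standard error under the null: sqrt(2 × 0.485 × 0.515 / 250) = 0.0447.
- Standard error under the alternative: sqrt((0.40 × 0.60 + 0.57 × 0.43) / 250) = 0.0441.
- z = (0.17 − 1.96 × 0.0447) / 0.0441 = 1.87, so power is 96.9%.

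This agrees with the stated figure of more than 90%. It has no bearing on flares, for which the SAP gives no rate, dropout or power.

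**Inputs for the tail (assumptions, not SAP figures).**

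- Share of patients without a closing SFI assessment: 5-10%.
- Unassessed tail: 4-12 weeks. Visit 4 (Week 4) to Visit 16 (Week 52) gives 12 intervals in 48 weeks, about 4 weeks each, so this is one to three visit intervals.
- Severe flares: 0.15 per patient-year.

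**Share of planned person-time** = share of patients × tail / 52.

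- Low: 0.05 × 4/52 = 0.4%.
- High: 0.10 × 12/52 = 2.3%.

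With the tail in the denominator, the estimated rate is (1 − share) times the rate without it, so rates fall by about the same 0.4-2.3%.

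**Severe flares expected in the tail, per arm** = 250 × share × 0.15.

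- Low: 250 × 0.05 × 4/52 × 0.15 = 0.14.
- High: 250 × 0.10 × 12/52 × 0.15 = 0.87.

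**Effect on the comparison, 10% v 5% such losses.**

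- 12-week tail: (1 − 0.10 × 12/52) / (1 − 0.05 × 12/52) = 0.9769 / 0.9885 = 0.988, a shift of 1.2%.
- 4-week tail: 0.9923 / 0.9962 = 0.996, a shift of 0.4%.
- Equal losses and tails: ratio 1, no shift.

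**A harsher set of assumptions.** Here flare times are exponential, 52-week severe-flare risk is 10-25%, dropout is 10-30%, and every dropout carries a tail of 2-12 weeks. The tail is then 0.4-8.0% of accrued person-time, and rates fall by the same proportion. With 15% risk, 20% dropout and an 8-week tail, the rate is 0.157 instead of 0.163 per year (−3.4%).

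Simulated Cox fits (60,000 per arm, 15% risk) compare the hazard ratio under the SAP rule with that from censoring at the last assessment:

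| Dropout, active v placebo | Tail (weeks) | Hazard ratio multiplied by |
|---|---|---|
| 20% v 20% | 8 | 1.000 |
| 30% v 15% | 8 | 0.971 |
| 30% v 15% | 12 | 0.957 |
| 15% v 30% | 12 | 1.047 |

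A 3-5% shift thus needs twice the dropout in one arm and a long tail for every dropout.

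**The case against.** The SAP does not say how a treatment or study discontinuation date is set for a lost patient. It may be the last visit or last contact, and the convention may sit in the protocol or the case report form instructions. The gap could then be small or nil. This stands: the rule permits unassessed time, but its amount is unknown.

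Many leavers have a closing visit. Section 6.3 provides for an early study termination visit, and a patient assessed on or after the end date has no tail. PPCV and PP also stop at treatment discontinuation and at prohibited-medication start, so a later assessment can cover the window. This stands too, and it makes the principal analysis less exposed than AC.

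The line about absent records may be only a data-entry convention for the flare form. That is a fair reading, but the exposure definition alone produces the excess time, and nothing in the SAP limits the convention to assessed time.

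Two stronger readings are tempting. One is that the end dates are mere paperwork dates, so that lost patients in general gain long flare-free periods. The SAP does not say so. The other is that the end of exposure in PPCV and PP may itself be imputed, because Section 6.13.1 mentions "imputation of missing last date on study drug". That section concerns the duration of drug exposure for safety. Nothing links it to the treatment discontinuation date in the flare definitions.

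Finally, if patients leave because they are worsening, censoring at the last assessment does not recover their flares. That is correct and limits what the fix can claim.

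**Conclusion.** The point holds as a defect of rule with a small expected effect. Flare exposure, and with it the Cox censoring time and the offset, is not tied to SFI assessment in any datapoint set, and no other part of the SAP supplies the link. For a patient whose last assessment precedes the end date and who has no later visit, the tail counts as flare-free.

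On 5-10% of patients affected and a 4-12 week tail, this is 0.4-2.3% of planned person-time, with flare rates lowered to match. The hazard or rate ratio shifts by about 1% only if losses differ by arm (10% v 5%, tail at the long end), and not at all if they are balanced. None of these inputs comes from the SAP, and none of the calculations models patients leaving because of a flare. The documents do not support a claim that the severe-flare result is materially biased.

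**What to change.** End flare exposure at the earlier of the existing end date and the date of the last visit with an SFI assessment. Any later assessed visit, including early termination, counts as covering the time before it. Use the resulting date in all three sets, for both Cox censoring and the log-exposure offset, and read an absent flare record as no flare only up to that date. State that patients with no postbaseline SFI assessment contribute no flare exposure, since the logarithm of a zero exposure is undefined. Keep the present rule as a sensitivity analysis.

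The cost is a wording change and one extra derived date, without new data. Time at risk falls slightly, and patients never assessed after baseline leave the flare models. The change removes unassessed person-time only. It does not deal with informative dropout.
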